### 7.9.2 Secondary Objective

To characterize change from baseline to 3 months post radiofrequency ablation in worst pain score in the past 24 hours in subjects treated for metastatic lesions in the periacetabulum, iliac crest, and/or sacrum, and for benign bone tumors

#### **Hypothesis**

There is no formal hypothesis. The objective is to characterize the change in pain.

#### **Data Collection and Endpoint Definition**

The data collection and endpoint definition are identical to the primary objective section.

#### **Analysis Methods**

Revision 1.0

Page 12 of 15

The main analysis for the secondary objective will be on the Secondary Objective Cohort and will use the Completers Analysis Set.

Descriptive statistics, as well as confidence intervals, of the change in pain will be reported.

Missing data imputation and sensitivity analysis using the Treated Analysis Set will be performed similar to the primary objective methods described in Section 0.

The subsets of subjects in the Secondary Objective Cohort (subjects with metastatic lesions outside the vertebral body and/or benign bone tumors) will be reported on as a whole, and also individually (metastatic lesions outside the vertebral body, benign bone tumors, and combinations of differing lesion types.)

### 7.9.3 Additional Measures

Revision 1.0

Page 13 of 15

### 7.10 Safety Evaluation

To characterize incidence of all device, procedure and/or therapy related adverse events and device deficiencies from enrollment to the 12-Month Visit.

### **Data Collection and Endpoint Definitions**

Reported adverse events and device deficiencies will be collected on eCRFs. They will be coded and summarized using the most recent Medical Dictionary for Regulatory Affairs (MedDRA).

Adverse event relationships will be collected for the study procedure, study therapy, OsteoCool system, and any other device. Relationship strength is categorized as (in order) Not Related, Unlikely, Possible, Probable, or Causal. Adverse events will be considered as "related" if any of the Possible, Probable, or Causal categories are indicated. Deaths will be collected on the Study Exit form and the Adverse Event form if applicable. The study will utilize an independent Clinical Events Committee (CEC) to adjudicate deaths to determine the relationship of the death to the device, procedure and/or therapy.

### **Analysis Methods**

The Treated Analysis Set will be included in the safety measures. Since adverse events were only reportable if they were related to the device, therapy and/or procedure, by definition no adverse events could occur prior to the RFA procedure. Therefore, there is no need to include the enrolled subjects not receiving the RFA procedure.

Adverse events will be presented in summary tables displaying the number of serious events, the number of events, the number of subjects with ≥1 event, and the percentage of subjects with ≥1 event. The events will be presented by MedDRA system organ class (SOC) and MedDRA preferred term (PT). The events will also be presented sorted in descending order of frequency overall. Adverse event tables will be displayed by study phase where applicable. Adverse events will be presented in aggregate as well as separated out by relationship to device, therapy and/or procedure. The analyses will also be

Revision 1.0

Page 14 of 15

presented by objective cohort. Adverse events may be reported using the classification system used by the Society of Interventional Radiology.

Subject exposure will be characterized. If many subjects discontinue prematurely, the event rates may be adjusted by follow-up time.

Analyses of deaths will be presented using the final CEC determination. Any difference between CEC determination and investigator reporting will be noted in the reports.

Device deficiencies will be presented in summary tables similar to adverse events.

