### 5. Investigation Plan

This is a prospective, multi-center, non-randomized, post-market, single arm study designed to provide effectiveness outcomes on the Medtronic OsteoCool™ RF Ablation system.

The start of the study for each subject is defined as the date the subject first signs the informed consent. Enrolled subjects who do not meet baseline eligibility or who do not undergo the OsteoCool procedure will be exited from the study (e.g. RF therapy was not delivered). The completion of the study for each subject is defined as the conclusion of the 12 Month Visit (Study Exit). Each subject's participation in the study is expected to last approximately 1 year from the date of the OsteoCool procedure. Each subject will be evaluated prior to the OsteoCool procedure, during the procedure, prior to hospital discharge, 3 days, 1 week, 1-, 3-, 6-, and 12-months post procedure.

There is no randomization in the study.

Revision 1.0

Page 5 of 15

After the sample size requirements for the primary objective hypothesis have been met, there will be a snapshot, and a *Primary Objective Report* will be prepared. The report will include testing of the primary objective hypothesis and only brief summaries of study subjects, non-primary objective efficacy and safety. The study will continue enrolling and following subjects after the report.

At the conclusion of the study, the data will be locked, and a *Final Study Report* will be prepared, which will include all evaluations (other than the primary objective). Additional subjects enrolled and treated for metastatic lesions involving only the vertebral body, that were not included in the Primary Objective Report will be combined with the subjects in the Primary Objective Report and summarized together in the Final Study Report. The primary objective will not be re-tested in this report. However, the results of the original primary objective hypothesis testing will be included for completeness.

Figure 5-1 outlines the study design and required follow-up requirements.

Revision 1.0

Page 6 of 15

[figure not shown]

Figure 5-1: Study Design

[figure not shown]

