### **Enrollment** Obtain informed Consent Baseline Verify eligibility criteria, obtain pregnancy test collect demographic, cancer history, baseline images at the target site(s) if available, Karnofsy Performance Scale (not for benign bone tumors), concomitant medications/treatments, BPI, EQ-5D-5L, EORTC-QLQ-C15-PAL (not for benign bone tumors), reportable adverse events/device deficiencies and deviations ≤21 days after baseline visit Enrollment, Baseline and RF ablation can occur on the same day OsteoCool Procedure Day 0 Collect RF ablation procedure and OsteoCool details, reportable adverse events/device deficiencies, deviations, concomitant medications/treatments, and Generator data uploads Study Was the RF therapy Discontinuation delivered? Yes **Prior to Discharge** Collect worst pain only, PI's self-assessment on local tumor control, post-treatment images (if available), deviations, and reportable adverse events/device deficiencies 3 days ± 2 Days after Day 0 1 week (7 days) ± 2 Days after Day 0 1-Month Visit 30 days ±15 Days after Day 0 3-Month Visit 90 Days ± 30 Days after Day 0 6-Month Visit 180 days ± 59 Days after Day 0 12- Month Visit 365 days ± 90 Days after Day 0

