### 7.1.3 Analysis Sets

#### **Analysis Sets**

There are 3 analysis sets:

**Enrolled**: all enrolled subjects. The demographics of this set, and specifically the subjects in this set but not in the Treated Analysis set, will only briefly be characterized. Otherwise, the efficacy and safety analyses will be on the following two analysis sets.

The analysis sets to be included in the efficacy analyses (primary objective, secondary objective, and additional measures) are described below.

**Treated Analysis Set**: all subjects who are successfully treated with the OsteoCool™ RF Ablation system.

**Completers Analysis Set**: the subset of Treated Analysis Set subjects who provided endpoint data at the 3-Month Visit. The Completers Analysis Set will be a subset of the Treated Analysis Set. The Completers Analysis Set will be the analysis population for the primary objective hypothesis testing.

The safety analyses will utilize the Treated Analysis Set.

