#### **Objective Cohorts**

There will be two objective cohorts, which will be used to separate the subjects to be analyzed in the primary objective versus the secondary objective. At the time of treatment with the OsteoCool™ RF Ablation system, subjects will get assigned to one of the two cohorts depending on the lesion type(s) treated. The two cohorts encompass the entire set of Treated Analysis Set subjects and are mutually exclusive. Each objective cohort will have a Treated Analysis Set and a Completers Analysis Set.

There will be a small number of subjects that are enrolled, but do not undergo the RFA procedure. They will not be assigned to an objective cohort.

**Primary Objective Cohort**: subjects with metastatic lesions involving the vertebral body only **Secondary Objective Cohort**: subjects with metastatic lesions outside the vertebral body and/or benign bone tumors. This includes subjects with a combination of lesions involving the vertebral body and outside the vertebral body. This cohort may get divided further depending on treatment site (for example: non-vertebral bone, benign bone tumors, combinations).

[figure not shown]

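### The SAP restricts the safety tables to successfully treated subjects where the CIP uses all enrolled, so events and device deficiencies from procedures aborted without RF delivery appear in no planned safety table

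*Combined protocol and SAP*

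**What the plan says.** The two documents name different safety populations. CIP 13.1.4 (Analysis Populations) and CIP 13.5.2 both assign the safety measures to the Enrolled population. SAP 7.1.3 states: "The safety analyses will utilize the Treated Analysis Set". It defines that set as subjects successfully treated with the system. SAP 7.10 repeats the choice and gives the reason. Only related events are reportable, so "by definition no adverse events could occur prior to the RFA procedure", and hence "Therefore, there is no need to include the enrolled subjects not receiving the RFA procedure".

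The safety measure in SAP 7.10 nevertheless covers related "adverse events and device deficiencies from enrollment to the 12-Month Visit". On deficiencies the same section says only: "Device deficiencies will be presented in summary tables similar to adverse events".

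The SAP expects some untreated subjects: "There will be a small number of subjects that are enrolled, but do not undergo the RFA procedure". SAP 7.1.3 gives them a brief demographic description and no objective cohort. SAP 7.11 declares that the planned analysis has not changed.

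**The concern.** The rationale in SAP 7.10 concerns the time before the procedure, but the exclusion it supports depends on whether treatment succeeded. A subject can undergo bone access and anesthesia, have the procedure aborted, and receive no RF energy. Such a subject has been exposed to the procedure and to device components, yet falls outside the Treated set.

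The stated measure is the incidence of all related events and all device deficiencies from enrollment. If the SAP is followed, those arising in aborted procedures are collected and then left out of the tables meant to give that incidence. For deficiencies the omission is tied to the outcome: a fault that prevents any RF delivery takes its own subject out of the table of faults. In a post-market device study, these are cases the safety section ought to show.

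**Working it through.** **Does the SAP's reason cover every subject it excludes?** Three kinds of enrolled subject can fall outside the Treated set or sit at its edge.

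| Subject | Can a reportable event or deficiency arise? | In CIP safety set? | In SAP safety set? |
|---|---|---|---|
| Exits after consent, no procedure started | A related event: no, as the SAP argues. A deficiency: not addressed by the SAP | Yes | No |
| Procedure started, aborted, no RF delivered | Yes | Yes | No |
| RF partly delivered | Yes | Yes | Unclear, because success is not defined |

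The second row rests on these provisions:

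- CIP 9.11 lists an aborted ablation without RF delivery as a reason for discontinuation. SAP 5 classes it with subjects "who do not undergo the OsteoCool procedure will be exited from the study (e.g. RF therapy was not delivered").
- CIP 11.2 makes events related to the access kit, probe or generator, and to surgery or anesthesia, reportable. None of these depends on RF delivery.
- CIP 11.3 takes failure to perform the procedure out of reporting only where there is no injury, so injury in a failed attempt was anticipated.
- CIP 11.2 collects all device deficiencies from enrollment to discontinuation.
- In SAP Figure 5-1 the Day 0 step reads "Collect RF ablation procedure and OsteoCool details, reportable adverse events/device deficiencies". The question whether RF was delivered comes after it. CIP Figure 6-1 has the same order.

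**Do the data reappear elsewhere in the SAP?** SAP 7.1.1 would show the exit and its reason, but not the event or deficiency. The by-cohort safety tables omit these subjects because they have no cohort.

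**Size.** The plan gives no figure to reproduce here. The only relevant number is 250 enrolled (SAP 6). The other inputs below are assumptions.

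Let N = 250 be enrolled, U untreated, T = N − U treated with event proportion p, and x the number of untreated subjects with an event.

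- Treated percentage = p
- Enrolled percentage = (pT + x)/N
- Enrolled minus Treated = (x − pU)/N

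With U = 15 and p = 3%, T = 235 and pT = 7.05:

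- x = 0: 7.05/250 = 2.82%, a difference of −0.18 points
- x = 1: 8.05/250 = 3.22%, a difference of +0.22 points

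In whole subjects, 7/235 = 2.98% Treated, against 7/250 = 2.80% or 8/250 = 3.20% Enrolled, which gives the same differences.

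For U from 5 to 25, p from 1% to 10%, and x of 0 or 1, the extremes are:

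- U = 25, p = 10%, x = 0: −2.5/250 = −1.00 points
- U = 5, p = 1%, x = 1: (1 − 0.05)/250 = +0.38 points

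Counts move in one direction only: the Treated count can never exceed the Enrolled count. The share of subjects with an event that is left out is x/(m + x), where m is the number of treated subjects with an event. With m from 5 to 20 and x of 1 or 2 (assumed), it runs from 1/21 = 4.8% to 2/7 = 28.6%. For example, with U = 5, m = 10 and x = 2, the SAP set gives 10/245 = 4.1% and the CIP set 12/250 = 4.8%, and 2 of the 12 affected subjects (16.7%) are not shown.

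**The case against.** The best defence is that little is lost. The events remain on case report forms and in reporting to the sponsor, ethics committees and authorities. CIP 13.1.6 and SAP 7.8 also plan annual safety reporting, for which no Treated restriction is stated. This stands as a limit: the gap is in the planned tables, not in data collection or oversight. It does not close the gap, because neither section specifies safety tables for the annual reports, and the SAP governs the Primary Objective and Final Study Reports.

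Second, successful treatment is undefined, and SAP 7.7 summarises technical success as a procedure-site characteristic, so some technical failures may be counted as treated. If RF was partly delivered, or delivered after a component was replaced, the subject continues in the study. That is fair. The group clearly affected is subjects with a started procedure and no RF delivery at all, a subset of an already small number.

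Third, the Enrolled denominator has its own fault. It includes consent-only exits, who contribute almost no follow-up, and the largest shift above (−1.00 points) is this dilution. This also stands, and it favours a separate column or listing over simply enlarging the denominator.

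Fourth, SAP 7.10 states the change openly, and CIP 13.1 allows changes that do not alter a principal feature without an amendment, provided the study report justifies them. No breach of that rule is shown. But the reason given does not cover aborted procedures or deficiencies, and SAP 7.11 says there is no change.

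**Conclusion.** The concern holds. The SAP narrows the CIP's safety population for a reason that does not apply to procedures aborted without RF delivery and does not address device deficiencies. Related events and deficiencies in those subjects would be collected but would enter no planned safety table.

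The effect on percentages is small under the assumptions shown: −1.00 to +0.38 points with 5 to 25 untreated, 1% to 10% in the treated, and no or one untreated subject with an event. The documents give none of these three inputs. The omission of individual events and deficiencies does not depend on them; it follows from the set definition whenever such a case occurs. The measure is descriptive and the primary hypothesis test is untouched. This should be fixed before the reports are produced, but it does not threaten the study's main conclusion.

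**What to change.** In SAP 7.1.3 and 7.10, do one of two things:

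- restore the CIP's Enrolled set for the adverse event and device deficiency tables; or
- keep the Treated tables and add a column or listing of every reportable event and deficiency in enrolled subjects without RF delivery, showing how many such subjects there were.

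The second option targets the gap directly and keeps consent-only exits out of the denominator. Either way, delete the argument that no event is possible by definition. If any departure from the CIP remains, record it in SAP 7.11 in place of the no-change statement and justify it in the study report, as CIP 13.1 requires.

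The cost is a few lines of SAP text and one column or listing. No new data are needed: CIP 9.11 requires a Study Exit form for every enrolled subject, and CIP 11.2 and 11.4 put each reportable event or deficiency on its own form. The reported safety counts may be slightly less favourable.

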### **6.** Determination of Sample Size

#### **Primary Objective Sample Size**

The sample size calculations were performed using PASS 11 statistical software. (PASS 11 v. 11.0.7, Hintze J).

The primary objective is to demonstrate an improvement from baseline to 3 months post radiofrequency ablation in worst pain score in the past 24 hours in subjects treated for metastatic lesions involving only the vertebral body.

The standard deviation of change from Greenwood et al (2015) is estimated to be 4.1 at 4 weeks. The standard deviation of change in the CAFE study Berenson et al (2011) was 3.2 at 1 month. The standard deviation of change from Lane et al (2011) is estimated to be 2.4 at 1 day post-procedure. It is not known which of those studies will most closely match the population and test conditions in this study. The median of those 3 studies is 3.2. To account for this study having a longer follow-up period and a more diverse patient population, and thus more opportunity for variability, the standard deviation for our sample size calculation will be increased to 3.5.

The minimal clinically important difference (MCID) of 2 points was used to interpret pain score differences in terms of clinical relevance in Bagla et al (2016) and a clinically significant change in pain of 2 points was also identified in Greenwood (2015). This will be used for our calculations.

Bagla (2016) followed subjects for 3 months post procedure. They reported that pain scores were provided for 68% of subjects (32% not provided) at 3 months. This will be used for our calculations.

The PASS program used to calculate the sample size was the one-sample t-test power analysis, mean0=0, meanA=2, standard deviation (of change) =3.5, two-sided significance level (alpha)=0.05, and power=0.90. The required sample size was 35. To account for subjects getting treated but not providing the 3-Month data, the treated sample size is adjusted for a 32% loss, to 52.

A sample size of 35 subjects successfully treated and completing the pain assessment at 3 months is expected to provide results that will be considered relevant to clinicians, as well as provide acceptable power to test the primary objective.

Sample size requirements were only calculated for the primary objective. There are no sample size requirements for the secondary objective and the additional objectives.

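### The 12-month adverse event incidence is a crude percentage of treated subjects, and adjustment for follow-up is optional and undefined although the plan sizes for 32% without month-3 data

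*Combined protocol and SAP*

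**What the plan says.** SAP 7.10 defines the safety measure as follows: "To characterize incidence of all device, procedure and/or therapy related adverse events and device deficiencies from enrollment to the 12-Month Visit". On the denominator it says "The Treated Analysis Set will be included in the safety measures". The tables show event counts together with "the number of subjects with ≥1 event, and the percentage of subjects with ≥1 event". They are given in aggregate, by relationship, and also "presented by objective cohort".

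Three sentences in SAP 7.10 bear on follow-up:

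- "Adverse event tables will be displayed by study phase where applicable". The phases and their denominators are not defined.
- "Subject exposure will be characterized". No method is given.
- "If many subjects discontinue prematurely, the event rates may be adjusted by follow-up time". No threshold is set, no estimator is named, and the verb is permissive.

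Protocol 13.5.2 plans the same kind of counts and percentages and has no adjustment for follow-up. Protocol 11.2 collects reportable events only until the subject discontinues.

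On expected loss, SAP 6 cites a vertebral-metastasis series: "They reported that pain scores were provided for 68% of subjects (32% not provided) at 3 months". It uses that 32% to raise 35 completers to 52 treated subjects. SAP 7.4 attributes missing month-3 data mainly to death, or to failing health that prevents contact. It does not split the two.

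**The concern.** A subject who leaves at month 2 stays in the denominator for ten further months in which no event can be recorded. If that subject died, this is correct for a cumulative incidence, because no later event was possible. If the subject was lost alive, later events are missed and the percentage is too low as a 12-month figure.

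The plan's only protection is a sentence whose trigger is undefined and whose use is optional, so the decision would be taken with the data in view. The sample size section already anticipates substantial month-3 loss in the primary cohort. The question could therefore be settled now.

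What is at stake is the 12-month safety statement. Protocol 13.1.1 justifies the enlarged enrollment partly by long-term follow-up, and protocol 4.1 notes that long-term outcomes with this system have not been studied. The percentages by objective cohort could also differ through follow-up alone.

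**Working it through.** **1. The plan's own figures.** A one-sample t-test with difference 2, SD 3.5 and two-sided alpha 0.05 has power 0.899 at n = 34 and 0.907 at n = 35, so 35 is right. Then 35/0.68 = 51.5, rounded up to 52. Both stated numbers reproduce, so the plan does size for 32% without month-3 data.

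**2. What that could mean for follow-up.** Treat the 32% as study loss (an assumption). The loss hazard is λ = −ln(0.68)/3 = 0.1286 per month.

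- If loss continues at this hazard, 0.68² = 46% remain at month 6 and 0.68⁴ = 21% at month 12. Mean follow-up is (1 − 0.214)/0.1286 = 6.1 months, or 51% of the year.
- If loss stops at month 3, 68% remain. Mean follow-up is (1 − 0.68)/0.1286 + 9 × 0.68 = 8.6 months, or 72%.

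**3. Crude percentage against cumulative incidence with death competing.** Assume a 12-month risk of 10% under full follow-up and a constant event hazard μ = −ln(0.90)/12 = 0.00878 per month. The crude percentage counts only events that occur before any loss. The cumulative incidence removes only deaths, so λ is replaced by its death component. With half of loss due to death, that component is 0.0643.

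*Loss continuing:* μ/(μ+λ) × (1 − e^(−12(μ+λ)))

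- Crude: 0.00878/0.13733 × (1 − 0.1924) = 5.2%.
- Cumulative incidence: 0.00878/0.07306 × (1 − 0.4162) = 7.0%.

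*Loss stopping at month 3:* μ/(μ+λ) × (1 − e^(−3(μ+λ))) + e^(−3(μ+λ)) × (1 − e^(−9μ))

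- Crude: 0.0216 + 0.6623 × 0.0760 = 7.2%.
- Cumulative incidence: 0.0237 + 0.8032 × 0.0760 = 8.5%.

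*Front-loaded events (80% of the risk in month 1):* the hazard is −ln(0.92) = 0.0834 in month 1 and ln(0.92/0.90)/11 = 0.0020 per month after that, integrated numerically.

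| Event timing | Loss after month 3 | Crude | Cumulative incidence, half of loss is death | Ratio |
|---|---|---|---|---|
| Constant hazard | continues | 5.2% | 7.0% | 0.74 |
| Constant hazard | none | 7.2% | 8.5% | 0.85 |
| 80% in month 1 | continues | 8.5% | 9.1% | 0.93 |
| 80% in month 1 | none | 8.9% | 9.4% | 0.95 |

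At the two extremes, if all loss is death the cumulative incidence equals the crude column in every row. If no loss is death it is 10% in every row.

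**4. Objective cohorts.** Assume 32% month-3 loss in both metastatic groups, 5% in benign tumors, hazards continuing to month 12, all loss censoring, and the same 10% risk at constant hazard. The crude percentage is 5.2% in metastatic and 9.1% in benign subjects. With the planned 100 and 50, the secondary cohort shows (100 × 5.2 + 50 × 9.1)/150 = 6.5%, against 5.2% in the primary cohort. With equal loss in all groups the gap is zero.

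**The case against.** The strongest reply is that this is a single-arm post-market study with a descriptive safety measure, no safety hypothesis, and several provisions that expose attrition. Exposure is to be described, disposition and discontinuations are summarized by visit (SAP 7.1.1), and adjustment is expressly foreseen. That stands: follow-up is not ignored, and the fault lies in how weakly the adjustment is committed. But describing exposure does not correct the percentage.

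A second reply is that related events cluster around the procedure, before much loss. This may well be so, and the last two rows of the table show that the gap is then small. The documents give no event timing, however. Protocol 11.3 removes several expected early surgical events from reporting within set windows, and protocol 11.2 includes events from repeat procedures, which can be late.

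Three stronger readings are tempting and are not supported:

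- **That a 10% risk would be reported as about half that.** This needs a constant event hazard, loss continuing at the same pace to month 12, and no deaths. The last conflicts with SAP 7.4, which names death among the main reasons for missing data.
- **That 32% is a discontinuation rate for the study.** It is the share of pain scores not provided in a cited series, applied to the primary cohort only. A subject without a pain score may still be followed for events, by phone if needed. No loss is stated for non-vertebral metastases, benign tumors or months 3 to 12.
- **That the cohorts cannot be compared.** The tables split by objective cohort, and the secondary cohort mixes metastatic and benign subjects. No formal comparison is planned, and the 5% benign loss used above is an assumption. All that can be said is that the percentages may differ through follow-up alone.

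**Conclusion.** The point holds in a limited form. The plan commits only to a crude percentage as its 12-month incidence, stops collecting events at discontinuation, anticipates 32% missing month-3 data in the primary cohort, and leaves adjustment optional, without a trigger and without a method. The crude percentage understates later events to the extent that loss is censoring.

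With a 10% risk and half of loss due to death, the shortfall ranges from about 0.5 to 1.9 percentage points across the four scenarios. It is zero if all loss is death and larger if little of it is. These figures rest on an assumed event rate, event timing, death share and later loss, and on reading missing pain scores as study loss. They illustrate scale and do not predict the result. The change is worth making because it is cheap and removes a choice that would otherwise be made after the data are seen.

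**What to change.** In SAP 7.10, replace the conditional sentence with a commitment to report:

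- the 12-month cumulative incidence of first related adverse event in the Treated Analysis Set, by the Aalen-Johansen estimator, with death as a competing event and censoring at study exit, with 95% confidence intervals, overall and by objective cohort;
- events per unit of person-time, overall and by objective cohort;
- the crude counts and percentages as now planned.

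If tables by study phase are kept, define the phases and use subjects at risk at the start of each as the denominator.

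The cost is a little more programming. Event dates are required by protocol 11.2 and a Study Exit form is completed for every enrolled subject, so no new data collection appears to be needed, provided that form carries the date of exit or death. The late-event estimate may be less favourable and less precise. The estimator also assumes that subjects lost alive have the same later event risk as those who stay. That is open to doubt when failing health causes the loss, so the reasons for exit should be shown beside it.
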